Appendix

Appendix A. Anticipated Adverse Events

1. Acute Respiratory Distress Syndrome (ARDS)	35. Laceration
2. Air embolism	36. Leakage of air or blood into the lungs or other organs due to perforation
3. Allergic reaction	37. Local hematoma/ecchymosis
4. Anemia	38. Mobile strands in the inferior vena cava
5. Anesthesia reaction	39. Myocardial infarction
6. Arrhythmias	40. Obstruction or perforation or damage to the vascular system
7. Atelectasis	41. Pericardial effusion
8. Atrio-Esophageal Fistula	42. Pericarditis
9. Atypical flutter	43. Phrenic nerve damage
10. AV fistula	44. Pleural effusion
11. Cardiac perforation/tamponade	45. Pneumonia
12. Cardiac Thromboembolism	46. Pneumothorax
13. Cerebrovascular accident (CVA)	47. Pseudoaneurysm
14. Chest pain/discomfort	48. Pulmonary edema
15. Complete heart block, temporary or permanent	49. Pulmonary embolism
16. Component damage to ICD or pacemaker	50. Renal Failure
17. Congestive heart failure	51. Respiratory depression/failure
18. Coronary artery dissection	52. Retroperitoneal hematoma
19. Coronary artery spasm	53. Rhabdomyolysis, including that produced by body position or propofol
20. Death	54. Seizure
21. Dislodgement of ICD or permanent pacing leads	55. Shortness of Breath
22. Endocarditis	56. Skin burns due to cardioversion, tape, etc.
23. Exacerbation of pre-existing atrial fibrillation, or other arrhythmia	57. Syncope/Dizziness
24. Expressive aphasia	58. Temperature elevation
25. Hair loss due to anesthesia	59. Thromboembolism
26. Heart failure	60. Transient ischemic attack (TIA)
27. Hematuria	61. Unintended complete/incomplete AV, sinus node or other heart block or damage
28. Hemorrhage	62. Urinary tract injury or infection related to the urinary catheter
29. Hemothorax	63. Valvular damage/insufficiency
30. Hypertension/Hypotension	64. Vasovagal reactions

31. Increase in frequency or duration of episodes of typical atrial flutter	65. Volume overload
32. Increased phosphokinase level	66. Worsening obstructive, restrictive, or other form of pulmonary disease
33. Infection, localized or systemic	67. X-ray radiation injury of skin, muscle or organ
34. Injury to skin, muscle, connective tissue due to body position, electrical cardioversion, etc.	

Appendix B. Definition of related hospitalization

Heart failure	Hospitalization event that meets ALL of the following criteria: 1. The patient was admitted to the hospital with a primary diagnosis of HF as the cause for hospitalization. 2. The patient's length of stay in hospital extended for at least 24 hours (or a change in calendar date if the hospital admission and discharge times are unavailable). 3. Diagnosis of HF by at least 1 of each of the following 3 criteria: symptom, sign, and medication (specifically for the treatment of worsening heart failure)/supportive measures/objective assessments.
Arrhythmia	When a patient was hospitalized for elective or urgent diagnosis or treatment of bradyarrhythmias, atrial, or ventricular rhythm disorders of the heart.
Transient ischemic attack and stroke	When a patient was hospitalized for elective or urgent diagnosis or treatment of TIA or stroke. TIA was defined as a transient episode of focal neurological dysfunction lasting for <24 hours caused by brain, spinal cord, or retinal ischemia, without acute infarction. Stroke was defined as an acute episode of focal or global neurological dysfunction caused by brain, spinal cord, or retinal vascular injury as a result of hemorrhage or infarction.
Myocardial infarction	When there was evidence of myocardial necrosis in a clinical setting consistent with myocardial ischemia, and required the combination of: 1. Evidence of myocardial necrosis (either a typical rise and fall in cardiac biomarkers or postmortem pathological findings); and 2. Supporting information derived from the clinical presentation, electrocardiographic changes, or results of myocardial or coronary artery imaging.
Other cause	CV A hospitalization not included in the above categories but with a specific, known cause (including but not limited to: hospitalization for unstable angina, pulmonary embolism or peripheral arterial/vascular disease, peripheral emboli, venous thrombosis, or other vascular reasons or complications).

Hospitalization for end point adjudication was defined as a nonelective admission to an acute care setting for medical therapy that results in at least a 24-hour stay (or a date change if the time of admission/discharge is not available).

Appendix C. Quality of life scale (EQ-5D-5L)

Patients will be asked to grade their Quality of Life, since the start of the study, using EQ-5D (The EuroQol Group. Health Policy 1990 December; 16(3):199-208).

	Tick one answer in each section
MOBILITY	
I have no problems in walking about	
I have slight problems in walking	
I have moderate problems in walking	
I have severe problems in walking	
I am unable to walk about	
SELF-CARE	
I have no problems washing or dressing	
I have slight problems washing or dressing	
I have moderate problems washing or dressing	
I have severe problems washing or dressing	
I am unable to wash or dress myself	
USUAL ACTIVITIES (e.g. work, study, housework family or leisure activities)	
I have no problems with performing my usual	
I have slight problems with performing my usual	
I have moderate problems with performing my usual	
I have severe problems with performing my usual	
I am unable to perform my usual	
PAIN / DISCOMFORT	
I have no pain or discomfort	
I have slight pain or discomfort	
I have moderate pain or	
I have severe pain or	
I have extreme pain or discomfort	
ANXIETY /	
I am not anxious or depressed	
I am slightly anxious or depressed	
I am moderately anxious or	
I am severely anxious or	
I am extremely anxious or	

[figure not shown]
Patients will also be asked to grade their state of health on the visual analogue scale.

“To help people say how good or bad their state of health has been **on average since starting the study**, we have drawn a scale (rather like a thermometer) on which the best state you can imagine is marked 100 and the worst state you can imagine is marked 0.

We would like you to indicate on this scale how good or bad your health has

been **on average since starting the study** in your opinion. Please do this by drawing a line on the scale."

Best imaginable
state of health

Appendix D. Atrial Fibrillation Effect on Quality-of-life (AFEQT) Questionnaire

Section 1. Occurrence of atrial fibrillation

Name or ID: _____

Are you currently in atrial fibrillation? Yes No

If No, when was the last time you were aware of having had an episode of atrial fibrillation? (Please check one answer which best describes your situation)

earlier today 1 month to 1 year ago
 within the past week more than 1 year ago
 within the past month I was never aware of having atrial fibrillation

Section 2. The following questions refer to how atrial fibrillation affects your quality of life.

On a scale of 1 to 7, over the past 4 weeks, as a result of your atrial fibrillation, how much were you bothered by: (Please circle one number which best describes your situation)

	Not at all bothered Or I did not have this symptom	Hardly bothered	A little bothered	Moderately bothered	Quite a bit bothered	Very bothered	Extremely bothered
1. Palpitations: Heart fluttering, skipping or racing	1	2	3	4	5	6	7
2. Irregular heart beat	1	2	3	4	5	6	7
3. A pause in heart activity	1	2	3	4	5	6	7
4. Lightheadedness or dizziness	1	2	3	4	5	6	7

On a scale of 1 to 7, over the past 4 weeks, have you been limited by your atrial fibrillation in your: (Please circle one number which best describes your situation)

	Not at all limited	Hardly limited	A little limited	Moderately limited	Quite a bit limited	Very limited	Extremely limited
5. Ability to have recreational pastimes, sports, and hobbies	1	2	3	4	5	6	7
6. Ability to have a relationship and do things with friends and family	1	2	3	4	5	6	7

On a scale of 1 to 7, over the past 4 weeks, as a result of your atrial fibrillation, how much difficulty have you had in: (Please circle one number which best describes your situation)

	No difficulty at all	Hardly any difficulty	A little difficulty	Moderate difficulty	Quite a bit of difficulty	A lot of difficulty	Extreme difficulty
7. Doing any activity because you felt tired, fatigued, or low on energy	1	2	3	4	5	6	7
8. Doing physical activity because of shortness of breath	1	2	3	4	5	6	7
9. Exercising	1	2	3	4	5	6	7
10. Walking briskly	1	2	3	4	5	6	7
11. Walking briskly uphill or carrying groceries or other items, up a flight of stairs without stopping	1	2	3	4	5	6	7
12. Doing vigorous activities such as lifting or moving heavy furniture, running, or participating in strenuous sports like tennis or racquetball	1	2	3	4	5	6	7

On a scale of 1 to 7, over the past 4 weeks as a result of your atrial fibrillation, how much did the feelings below bother you? (Please circle one number which best describes your situation)

	Not at all Bothered	Hardly bothered	A little bothered	Moderately bothered	Quite a bit bothered	Very bothered	Extremely bothered
13. Feeling worried or anxious that your atrial fibrillation can start anytime	1	2	3	4	5	6	7
14. Feeling worried that atrial fibrillation may worsen other medical conditions in the long run	1	2	3	4	5	6	7

On a scale of 1 to 7, over the past 4 weeks, as a result of your atrial fibrillation treatment, how much were you bothered by: (Please circle one number which best describes your situation)

	Not at all bothered	Hardly bothered	A little bothered	Moderately bothered	Quite a bit bothered	Very bothered	Extremely bothered
15. Worrying about the treatment side effects from medications	1	2	3	4	5	6	7
16. Worrying about complications or side effects from procedures like catheter ablation, surgery, or pacemakers therapy	1	2	3	4	5	6	7
17. Worrying about side effects of blood thinners such as nosebleeds, bleeding gums when brushing teeth, heavy bleeding from cuts, or bruising.	1	2	3	4	5	6	7
18. Worrying or feeling anxious that your treatment interferes with your daily activities	1	2	3	4	5	6	7

**On a scale of 1 to 7, overall, how satisfied are you at the present time with:
(Please circle one number which best describes your situation)**

	Extremely satisfied	Very satisfied	Somewhat satisfied	Mixed with satisfied and dissatisfied	Somewhat dissatisfied	Very dissatisfied	Extremely dissatisfied
19. How well your current treatment controls your atrial fibrillation?	1	2	3	4	5	6	7
20. The extent to which treatment has relieved your symptoms of atrial fibrillation?	1	2	3	4	5	6	7

Name or ID: _____

Appendix E. Well-being Questionnaire for Operating Room Staff

Basic Information

1. **Position:**

Lead operator Assistant Nurse Anesthesiologist Technician

2. **Procedure duration:** _____ hours _____ minutes

3. **Order of the case today:** No. _____

4. **Personal protective equipment (select all that apply):**

None Lead apron Lead cap Thyroid collar Lead skirt Lead glasses Dosimeter

1. Physical Discomfort and Pain Assessment

1.1 Do you experience any physical discomfort or pain?

No → *Proceed to Section 2 Radiation Exposure and Protection* Yes

1.2 Please select the affected body region(s) or symptom(s):

Headache Neck pain Shoulder pain

Back pain Low back pain Elbow discomfort

Hand discomfort Leg fatigue/stiffness Eye strain/dryness

General fatigue Emotional distress/irritability Other: _____

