Secondary endpoint	
 • The initial success of the procedure. • The proportion of intraoperative conversion to using X-ray. • Utilization of lead personal protective equipment (PPE) and wear time. • Quality-of-life for staff at the end of each procedure. • The proportion of patients with recurrence of AF/AFL/AT during the first 90 days post-ablation. • Early recurrence of atrial arrhythmias, defined as any AF/AFL/AT episode lasting >30 seconds occurring during the blanking period. • Late recurrence of atrial arrhythmias, defined as any documented AF/AFL/AT episode lasting >30 seconds occurring after the blanking period and up to 12 months. • Impact of early recurrence on late recurrence, assessed through survival analysis and multivariable adjustment to evaluate whether early recurrence predicts

	
subsequent late recurrence.
 
 • AF burden, assessed by scheduled rhythm monitoring (e.g., 7-day Holter at 3, 6, 9, and 12 months), expressed as the proportion of time spent in AF during the monitoring period. • Incidence of peri-procedural complication. • Total procedure duration, ablation time. • Changes in quality-of-life
Data Collection	
Three case report forms will be used to collect essential data
 
Case Report Forms Include:
 
 1. Procedure Form 
 • Patient-specific details • Procedural and ablation data, including de-identified Carto case backup data • Complications/adverse events during the procedure 2. Complications/Adverse Events Form 
 • Adverse events that occur after the patient leaves the procedure room through discharge • Adverse events from the discharge date through 7 days post-procedure • Adverse events from day 8 through day 90 post-procedure 3. Effectiveness Form 
 • For patients with atrial fibrillation, follow-up will be performed at 1 month, 2 months, 3 months, 6 months, 9 months and 12 months post ablation. Patients' symptoms and 12-lead ECG will be recorded at each follow-up visit to assess recurrence, and a 7-day

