1.1.2 Fluoroscopy related health risks and occupational injuries

Historically, fluoroscopy has been the standard for guiding EP interventions; however, despite advancements that have reduced radiation exposure to safer levels⁷⁻¹⁰, the need for heavy personal protective equipment (PPE) remains a significant concern. Prolonged use of leaded PPE has been linked to chronic occupational injuries such as back, neck, and other joint pain, as well as more serious conditions like spinal disc herniation^{11, 12}. These injuries are particularly concerning for healthcare providers who perform complex and lengthy procedures, potentially limiting their career longevity^{13, 14}.

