1.3 Pain intensity (VAS 0–5): **Your score:** _____

0 = No pain 1 = Mild 2 = Moderate 3 = Severe 4 = Very severe 5 = Unbearable

1.4 Do you need to rest briefly before resuming work? (0–4 scale) **Your score:** _____

0 = Not at all, full of energy 1 = Slight, quick recovery 2 = Moderate, recovers after short rest 3 = Marked, needs clear rest 4 = Severe, must rest before continuing

2. Radiation Exposure and Protection Assessment

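### Appendix E skips the need-for-rest item for staff who report no discomfort, so that score exists only for a subset selected after randomisation (minor)

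*Protocol*

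**What the plan says.** The synopsis lists a staff measure among the secondary endpoints, "Quality-of-life for staff at the end of each procedure", and Protocol section 3.4.2 lists a staff well-being survey. Appendix E is the form.

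- **Header:** role, procedure duration, the position of the case in the day's list, and protective equipment worn.
- **Item 1.1:** "1.1 Do you experience any physical discomfort or pain", answered No or Yes. It gives no reference period and does not mention the case just finished.
- **Routing:** No leads to "Proceed to Section 2 Radiation Exposure and Protection". Items 1.2, 1.3 and 1.4 are passed over.
- **Item 1.2 (Yes only):** body regions and symptoms. The list goes beyond pain and ends with "General fatigue Emotional distress/irritability Other".
- **Item 1.3 (Yes only):** pain intensity, "0 = No pain 1 = Mild 2 = Moderate 3 = Severe 4 = Very severe 5 = Unbearable".
- **Item 1.4 (Yes only):** "1.4 Do you need to rest briefly before resuming work", scored 0 to 4. Its zero category describes a person who needs no rest at all and feels energetic.

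Protocol section 1.1.2 gives the occupational background: "Prolonged use of leaded PPE has been linked to chronic occupational injuries such as back, neck, and other joint pain".

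**The concern.** Items 1.3 and 1.4 each have a zero category written for people without the problem, yet the routing removes most of those people before they reach the scale. Whether 1.4 is answered depends on item 1.1, which is completed after the procedure. By the protocol's own rationale, working without lead may change that answer. A comparison of recorded 1.4 scores is therefore not a comparison of the randomised groups.

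The second weakness is attribution. Section 1.1.2 describes chronic back, neck and joint pain in this workforce. A person with long-standing pain, or pain left from an earlier case that day, can answer Yes after a case in either lab.

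At stake is how far the staff well-being endpoint can show a benefit, or the lack of one, from working without fluoroscopy.

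**Working it through.** The protocol gives no figure on this point, so there is none to reproduce. The check follows the routing and then illustrates its effect. **All rates and means below are assumptions.**

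**1. What is recorded.** Let p be the proportion answering Yes in an arm, m the mean score among them, and u the mean that those answering No would have given. The all-staff mean is

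p × m + (1 − p) × u.

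The form supplies p and m. For item 1.3, u = 0, because a person with no discomfort or pain has no pain. For item 1.4, u may lie anywhere from 0 to 4, and no response in either arm informs it.

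**2. Item 1.3 can be repaired.** Differences are DSA minus non-fluoroscopic.

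| Yes, DSA vs non-fluoroscopic | Mean among Yes | Difference among Yes | Difference over all staff, No = 0 |
|---|---|---|---|
| 40% vs 20% | 2.0 vs 2.0 | 0.0 | 0.40×2.0 − 0.20×2.0 = 0.40 |
| 40% vs 30% | 2.0 vs 2.0 | 0.0 | 0.40×2.0 − 0.30×2.0 = 0.20 |
| 40% vs 20% | 2.0 vs 2.3 | −0.3 | 0.40×2.0 − 0.20×2.3 = 0.34 |

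Scoring No as 0 restores the all-staff comparison from data already on the form.

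**3. Item 1.4 cannot be repaired.** A simulation used 1,000,000 draws per arm. Latent discomfort x is normal with SD 1, and the answer is Yes if x > 0. Need for rest is 0.5x + √0.75·z + 1 with z standard normal, rounded and limited to 0–4, so latent rest and discomfort correlate at 0.5. Three pairs of arm means for x were tried.

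| Mean of x, DSA / non-fluoroscopic | Yes, DSA / non-fluoroscopic | True difference (all answer) | Among Yes only | No set to 0 |
|---|---|---|---|---|
| 0 / −0.5 | 50.0% / 30.9% | 0.204 | 0.075 | 0.295 |
| 0 / −1.0 | 50.0% / 15.8% | 0.389 | 0.131 | 0.504 |
| 0.5 / −0.5 | 69.2% / 30.9% | 0.426 | 0.180 | 0.638 |

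Restricting to Yes understates the difference and zero-filling overstates it. In the first row, with nothing assumed about u, the all-staff difference is 0.295 + 0.500·u(DSA) − 0.691·u(non-fluoroscopic), where 0.691 = 1 − 0.309. With each u between 0 and 4, this runs from 0.295 − 2.764 = −2.469 to 0.295 + 2.000 = 2.295. Imputation would have no observed 1.4 value from anyone answering No to build on.

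**4. Attribution.** Suppose a fraction c of responses would be Yes in either lab because of existing pain, and the rest answer Yes with probability q. The Yes proportion is c + (1 − c)q, so the difference between arms is (1 − c) × [q(DSA) − q(non-fluoroscopic)]. It shrinks by the factor 1 − c but keeps its sign.

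**The case against.** The form is not detached from the procedure. The synopsis sets the survey at the end of each case, and the header records duration, case order and equipment worn, so carry-over can at least be examined. What is missing is an attribution in item 1.1 itself.

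Item 1.1 asks about discomfort as well as pain, and fatigue appears among the symptoms in 1.2. A tired person may therefore answer Yes and reach 1.4. That stands, and it narrows the gap to staff who answer No but would still want rest. It does not close it, because fatigue is first mentioned after the Yes answer, under a heading about physical discomfort and pain.

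A reader might infer that the trial will compare scores only among staff who report discomfort. The protocol does not say so. Its statistical section is general, and a rule scoring 1.3 as 0 for No could properly sit in a statistical analysis plan. Item 1.1 is asked of everyone, so the proportion reporting discomfort can be compared without selection.

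A reader might also infer that a true benefit could be reversed and the result left uninterpretable. Assumed inputs can produce this for 1.3: Yes in 50% with mean 1.8 against 20% with mean 2.5 favours DSA among those answering Yes, although the all-staff means are 0.50×1.8 = 0.90 and 0.20×2.5 = 0.50. The reversal needs both a higher mean put in for the non-fluoroscopic arm and a Yes-only comparison that the document does not plan. With equal means the Yes-only difference is 0, and existing pain dilutes rather than reverses.

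Nor is this survey the only measure of benefit to staff. Use and wear time of lead protection is a separate secondary endpoint, and Section 2 of the form is reached by everyone.

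**Conclusion.** The point holds in a limited form. Need for rest is unrecorded for every staff member who answers No at 1.1, and no analysis rule can recover it; this follows from the routing alone. That the recorded subset differs between arms is a reasonable expectation from section 1.1.2, not a fact in the document. Under the assumed inputs, 1.4 differences of 0.20 to 0.43 points on a 0–4 scale read as 0.08 to 0.18 or as 0.30 to 0.64, depending on the workaround. The missing attribution in 1.1 tends to dilute a difference, provided existing pain is similarly common in both arms.

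Pain intensity is not lost, since No can be scored 0. The effect is confined to one secondary staff endpoint; sample size and both primary endpoints are untouched. This is a minor improvement that could be made, not a condition for the trial's validity.

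**What to change.** In Appendix E:

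1. Route No at item 1.1 to item 1.4, then to Section 2, so that all staff answer 1.4 after every case.
2. State that No at 1.1 scores 0 on item 1.3.
3. Compare 1.3 and 1.4 over all responses, not only those with Yes at 1.1.
4. Keep the wording of 1.1. For those answering Yes, add one tick: new or worsened during this procedure, yes or no. Count it over all responses, with No at 1.1 counted as not new.

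Rewording 1.1 itself to new or worsened pain is best avoided. A person with unchanged chronic pain would then answer No and be recorded as having no pain on 1.3, and forms already completed would no longer be comparable on 1.1 and 1.3.

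**Cost:** one or two extra answers per person per case, and no patient burden. Item 1.4 from forms already completed exists only for those who answered Yes and should be reported separately from the revised form.

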1.3 Pain intensity (VAS 0–5): **Your score:** _____

0 = No pain 1 = Mild 2 = Moderate 3 = Severe 4 = Very severe 5 = Unbearable

1.4 Do you need to rest briefly before resuming work? (0–4 scale) **Your score:** _____

0 = Not at all, full of energy 1 = Slight, quick recovery 2 = Moderate, recovers after short rest 3 = Marked, needs clear rest 4 = Severe, must rest before continuing

2. Radiation Exposure and Protection Assessment

2.1 Level of concern about radiation exposure (0–10): **Your score:** _____

0 = Not concerned → 10 = Extremely concerned

2.2 Do you think radiation protection measures affect your health?

Not at all Slightly Considerably Severely

2.3 Do you monitor radiation dose per procedure?

Always Sometimes Never

2.4 If fluoroscopy-free procedures without heavy protective gear are available, would you choose them? Yes No
